***Fluoroscopic swallow study:***

Swallowing function and physiology will be assessed using high-resolution digital fluoroscopy at a pulse rate of 30 frames per second, digitally stored for retrieval and offline analysis. Participants will be seated in the lateral viewing plane. Three trials each of the following swallowing tasks will be performed: Thin hold of 10 – 20mL liquid barium administered via cup, 5-10mL of pudding-thick barium administered via spoon, and 3-oz thin liquid sequential swallow administered by cup. Should aspiration be observed on the thin liquid swallows, we will omit the third trial and administer the pudding. Should aspiration occur with the pudding bolus, we will omit the remaining boluses (bail-out criteria). This protocol was selected because it mirrors our clinical protocol, and thus it would be possible to reduce participant burden and radiation exposure by replacing a clinical study with a research study, or vice-versa.

Our primary swallowing outcome measure will be score on the penetration-aspiration scale (PAS) measured from the videofluoroscopic evaluations of swallowing. Our secondary swallowing outcome measures will provide metrics of swallow physiology including swallow reaction time (SRT; H1 to B1), duration of laryngeal vestibule closure (dLVC; LVC to LVO),

duration to laryngeal vestibule closure (LVC) from hyoid burst (H1) (dtLVC\_H1), duration to LVC from bolus head in pharynx (B1) (dtLVC\_B1) and pharyngeal transit time (PTT; B1 to B2).

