### **Protocol 2 (aim 4)**

**Participants:** This study will include men and women with PD, and we will recruit from those participating in protocol 1, in addition to the general PD population at UF Fixel Institute for Neurological diseases given protocol 2's larger required N. For participants who did complete protocol 1, the procedures will not be replicated in protocol 2 (therefore these participants would only complete the 2nd and 3rd protocol 2 visits). The inclusionary and exclusionary criteria will be identical to those of protocol 1, with the exception that this protocol will also include people with possible or probable progressive supranuclear palsy (PSP) or multiple systems atrophy (MSA).

**Power Analysis:** To test the hypothesis that the relationship between swallow and cough motor deficits, and reflex cough sensitivity varies as a function of disease duration in PD, we would compare the penetration/aspiration scale change from baseline with 10 to 18 months apart for PD patients. As shown in our pilot study data, the mean (SD) penetration-aspiration scale change from baseline for the first two 10 to 14 months period are 2.08 (1.97) and 2.82 (2.33), respectively. Based on it, to reach a 0.85 power by controlling the type I error rate to 0.05 for detecting this effect size with two-sided test, we would need 155 PD patients.

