### **Procedures unique to protocol 2:**

Longitudinal measurement of swallowing and cough function: Measures of swallowing and cough will be collected at 3 time points spaced 10 – 18 months apart.

For participants who were also in study protocol 1, those swallowing and cough data will be used for the first time-point in order to reduce participant burden.

Longitudinal measures of Participant disease status: Disease severity (unified Parkinson's disease rating scale and Hoehn & Yahr score), medications, levodopa equivalent dose, and surgical status (specifically deep brain surgery) will be recorded at each study visit.

Pharmacologic and/or surgical therapies for PD may have known and unknown influences on swallowing and/or cough function (i.e., (43)) and will therefore be recorded for this study.

Swallow and cough outcome measures (described in detail in protocol 1):

1. Slope of UtC sensitivity
2. Cough sensitivity: Capsaicin concentration that elicits the 2-cough response (C2)
3. Cough motor (airflow) measures: CPD, PEFR, PEFRT, CVA
4. Swallowing performance measures: Penetration-aspiration scale scores (PAS)
5. Swallowing physiology measures: SRT, dtLVC\_H1, dtLVC\_B1, dLVC, PTT

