**Statistical analysis:** In the statistical analysis, we would fit a linear mixed effects model to take into account the repeated measurement by regarding each subject as a cluster. Specifically, in the analysis, the repeatedly measured outcome, i.e. change of penetration-aspiration scale scores (PAS), C2, cough and swallowing physiology variables from baseline, will be fitted by adjusting for fixed effects terms including baseline PAS, age, sex, medications, levodopa equivalent dose, surgical status, and disease duration (2=third 10-18 month; 1=second 10-18 month; and 0=first 10-18 month) and the random effects term due to participants. Restricted resampling model selection (Zou et al. 2015) technique will be adopted to conduct the valid statistical inference for repeated measurement data and it is also robust to missing data which is particularly useful for this study. **Expected outcomes:** Results of this aim are expected to provide a clinical deliverable in the form of sensitive and specific predictor(s) of airway protection dysfunction that are more customized for patients with different PD durations. As well, because of the study's prospective longitudinal design, this study will also be the first to examine the natural history of cough function in people with PD over the proposed 3-year time period.

**Data storage:** All participant records will be maintained in HIPPA compliant storage. Paper copies of the ICF will be kept in a locked cabinet, in the locked research laboratory of the PI (D2-063 or DG-143; [name]). Paper data collection forms will be kept in a separate, locked file cabinet, also in the research laboratory of the PI. Paper forms will not include participant names or dates; rather participants will be assigned a unique participant ID number that will be kept separate from the name. Electronic database files containing summary data for individual participants and compiled data for all participants will be saved according to participant number within a limited access, password protected folder on the PI's P-drive.

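### Protocol 2 credits model selection with robustness to missing data and states no follow-up of leavers and no sensitivity analysis; PAS change is understated if loss depends on unseen worsening

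*Combined protocol and SAP*

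**What the plan says.** Under Procedures unique to protocol 2: "Measures of swallowing and cough will be collected at 3 time points spaced 10 – 18 months apart". The same section lists disease severity, medications and levodopa dose among the items for which, ending with the surgical item, the wording is "surgical status (specifically deep brain surgery) will be recorded at each study visit".

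The Statistical analysis paragraph of Protocol 2 specifies a linear mixed effects model, "regarding each subject as a cluster". The outcome is change from baseline. The fixed effects include baseline PAS, age, sex, medications, levodopa dose, surgical status and period, and there is a participant random effect. Restricted resampling model selection is added, and of that technique the plan says "it is also robust to missing data which is particularly useful for this study".

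The Power Analysis uses pilot PAS changes that "are 2.08 (1.97) and 2.82 (2.33), respectively". It aims "to reach a 0.85 power by controlling the type I error rate to 0.05 for detecting this effect size with two-sided test" and concludes "we would need 155 PD patients".

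The supplied text contains no missing-data assumption, no sensitivity analysis, no recording of deaths or reasons for leaving, no procedure for participants who miss visits and no attrition allowance. The Fluoroscopic swallow study section does allow "replacing a clinical study with a research study, or vice-versa", for reasons of burden and radiation; it does not connect this with missed visits.

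**The concern.** The plan expects missing data and answers it with a property that the named technique does not have. Model selection decides which covariates enter a model fitted to the observed rows. It says nothing about the rows that are absent.

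Two features make this matter here. First, the outcome is change from baseline, so a participant seen only at visit 1 supplies no outcome, and one lost after visit 2 supplies only the earlier change. Second, the Background describes high rates of aspiration pneumonia in PD, and Protocol 2 also admits people with PSP or MSA. Deterioration between visits, not captured at any earlier visit, is a plausible reason for not returning.

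If that happens, the visit 3 change and the contrast between periods are biased towards zero, and the natural-history conclusions describe those still able to attend. A larger sample would not cure this.

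**Working it through.** **Inputs from the Power Analysis.** First change 2.08 (SD 1.97), second change 2.82 (SD 2.33), read as the changes from baseline at visits 2 and 3. Contrast: 2.82 − 2.08 = 0.74. Power 0.85, two-sided 0.05.

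**Reproducing the 155.**
- Paired comparison with zero correlation: SD of the difference = √(1.97² + 2.33²) = √9.3098 = 3.051. The t-based size is 154.6, so 155, an exact match.
- Two-sample reading with pooled SD √(9.3098/2) = 2.158: 153 per group (normal) or 154 (t-based).
- On either reading no attrition allowance is visible. Keeping 155 evaluable would need 155/0.9 → 173, 155/0.8 → 194 or 155/0.7 → 222 enrolled at 10%, 20% or 30% loss.

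**Assumed, because the documents give no figure.** Correlation between a participant's two changes 0.3 to 0.7; loss before visit 3 of 10 to 30%; logit(loss) = a + b × PAS change, with b = 0.2 or 0.4 per point and a set to give the loss rate. Changes are simulated as bivariate normal and analysed by a random-intercept model of change on period, without other covariates.

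| Loss depends on | Loss before visit 3 | Estimated contrast (true 0.74) | Share of 0.74 lost |
|---|---|---|---|
| Unseen second change | 10% | 0.56 to 0.68 | 8 to 24% |
| Unseen second change | 20 to 30% | 0.23 to 0.61 | 18 to 69% |
| Observed first change only | 10 to 30% | 0.69 to 0.73 | 1 to 7% |

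The last column is 1 − estimate/0.74; for example 1 − 0.61/0.74 = 18%. Repeated runs moved the lowest values by 0.01 to 0.02 (0.22 for 0.23, 0.67 for 0.69).

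**Does a richer covariance help?** A maximum-likelihood fit with unstructured covariance was run with the odds of loss doubling per SD of the unseen second change, that is log(2)/2.33 = 0.30 per PAS point, the middle of the range above. The contrast was 0.59 to 0.66 at 10% loss, 0.47 to 0.58 at 20% and 0.34 to 0.50 at 30%. When loss depended on the observed first change, the visit 3 mean was recovered as 2.81 to 2.83 against 2.82, while the plain mean of completers fell to 2.51 to 2.77. So the dropout mechanism decides the bias, and the covariance structure does not remove it.

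**Loss after visit 1.** If 20 to 30% are lost with b = 0.2 to 0.4 on the unseen first change, the observed mean first change falls from 2.08 to 1.66 to 1.93. The level of change is understated. The effect on the contrast was not established, because both period means are affected.

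**The case against.** The strongest reply is that the plan does not rest on model selection alone. A likelihood-based mixed model with baseline PAS keeps partial records and is valid when loss is explained by modelled, observed data. This stands, and the third row of the table shows it. It is not enough that worsening participants leave; the understatement needs loss that depends on worsening no visit recorded.

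A reader might infer that nothing is collected once a participant stops attending. The documents do not say so. They tie collection to visits and are silent on leavers; the consent pages are not available, and clinical and research fluoroscopy may replace one another.

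A reader might also infer that the study could never detect selective loss. That is too strong: visit 1 and 2 PAS, cough and disease-severity data allow leavers to be compared with completers. Such a comparison is evidence, but it cannot rule out dependence on unseen values.

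Nor should the missing attrition allowance be read as proof of low power. With positive correlation a paired comparison needs fewer than 155 (t-based: 110 at correlation 0.3, 80 at 0.5, 50 at 0.7).

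Finally, the simulation omits the planned covariates, and its loss rates and mechanism are assumptions. That limits the figures. It does not supply the robustness that the plan claims.

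**Conclusion.** The point holds in a conditional form. The robustness claim is unsupported, and Protocol 2 states neither data collection for participants who miss visits nor a missing-data sensitivity analysis. The planned mixed model is a real but partial safeguard: close to unbiased for loss after visit 2 driven by observed change, biased for loss driven by unseen worsening, and without any outcome from participants lost after visit 1.

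In the unseen-worsening case the loss ranges from about a tenth of the 0.74 contrast (10% loss, weak dependence) to about two thirds (30% loss, strong dependence, low correlation). These are illustrations under assumed inputs. The documents do not show that such loss will occur, so a definite percentage of understatement should not be read from them. Because attended visits cannot settle which mechanism operates, a sensitivity analysis is needed in place of an assertion.

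**What to change.** **Statistical analysis, Protocol 2.**
- Delete the claim that model selection is robust to missing data. State that the primary mixed model assumes data are missing at random.
- Model PAS at all three visits with visit 1 as a response, so that baseline-only participants stay in.
- Add a sensitivity analysis that shifts the missing PAS of living participants who stopped, for example by +0.5, +1 and +2 points, and report when the conclusion changes. The visit 3 mean moves by (fraction missing) × (shift): at 20% missing, by 0.10, 0.20 and 0.40 points, to be judged against 0.74.
- Report deaths separately and do not impute PAS after death.

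**Procedures unique to protocol 2.**
- For participants who miss a visit and have not withdrawn permission for record use, review the medical record in the visit window for vital status, aspiration pneumonia, tube feeding, Hoehn & Yahr stage and reason for stopping.
- Compare leavers with completers on visit 1 and 2 data.
- Use PAS from a clinical fluoroscopy in the window only in a sensitivity analysis, flagged by whether symptoms prompted the scan. Scans done because of symptoms could bias PAS upward if entered as the visit value.

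**Cost.** Some coordinator time for a record review that staff already carry out at entry, possibly a consent line for continued record use, and one or two added analyses. No new procedure on participants is needed.

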## 7. Possible Discomforts and Risks

Completion of the Beck Depression Index-II (BDI-II) and Starkstein Apathy Scale (AS) may make some participants feel uncomfortable or sad. We will provide participants whose scores fall outside the norm with contact information for UF psychiatry and psychology for further evaluation and care if desired.

Some participants may find breathing against a resistive load and/or through a mouthpiece to be effortful or difficult and may report feeling breathless. We will instruct the participants to “relax and breathe” as well as provide breaks to allow them to breath naturally without the mouthpiece in place throughout the tasks.

Delivery of capsaicin has been found to be safe, reliable, and reproducible in multiple research studies involving both healthy and disordered populations. Although risks associated with capsaicin are low, participants may report a ‘tingling’ or ‘hot’ sensation that passes quickly with the swallowing of water. Thus, water will be available throughout study procedures.

Completion of a fluoroscopic swallow study involves patient exposure to radiation. However, we will minimize the amount of radiation exposure according to standard clinical practice: thoroughly explaining the protocol to the patient prior to the study and engaging the fluoroscopy only when the patient is completing each swallowing task. In addition, our protocol allows for the substitution of a clinical fluoroscopic swallow study with a research study, or vice-versa, to reduce unnecessary participant burden and radiation exposure.

For the SEP procedure, the EEG net that will be placed on the patient’s head will be soaked in an electrolyte solution prior to placement. As such, the patient’s head and hair may become damp. We will place clean dry towels around the patient’s shoulders to keep any excess moisture from seeping into their clothes and provide additional towels to dry off their hair following completion of the procedure.

## **8. Possible Benefits**

For most participants, there are no direct benefits for participating in this study. However, completion of a fluoroscopic swallow study, if one has not yet been completed as a part of his/her normal clinical care, may identify signs and symptoms of dysphagia and/or aspiration, with subsequent referral for appropriate management.

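### Swallowing or cough management between visits is neither recorded nor handled in Aim 4, although a study fluoroscopy may lead to referral for it, so Aim 4 changes may partly reflect treatment

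*Combined protocol and SAP*

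**What the plan says.** Section 8 (Possible Benefits) states that, for participants who have not already had a fluoroscopic swallow study in normal care, the study examination "may identify signs and symptoms of dysphagia and/or aspiration, with subsequent referral for appropriate management".

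Protocol 2 (Procedures unique to protocol 2) measures swallowing and cough at three time points, 10 to 18 months apart. For people who took part in Protocol 1, that examination supplies the first time point. Besides disease severity, "medications, levodopa equivalent dose, and surgical status (specifically deep brain surgery) will be recorded at each study visit". The reason given is that "Pharmacologic and/or surgical therapies for PD may have known and unknown influences on swallowing and/or cough function".

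The mixed model for change from baseline has "fixed effects terms including baseline PAS, age, sex, medications, levodopa equivalent dose, surgical status, and disease duration", plus a random participant effect. Eligibility is that of Protocol 1, widened to PSP and MSA. Neither list of criteria mentions swallowing or cough therapy.

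The expected-outcomes text then says that "this study will also be the first to examine the natural history of cough function in people with PD" over the three-year period.

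**The concern.** The plan accepts that treatment can alter swallowing and cough, and records PD drugs and surgery for that reason. It leaves out management aimed directly at swallowing or cough, which is also the treatment that the study's own examination can set in motion.

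The selection runs through the outcome. A poor swallowing result at one visit makes management before the next visit more likely. If management works, later scores in the worst swallowers improve, and the observed change mixes disease course with treatment. Three things are exposed:

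- the estimated change in PAS and swallow physiology;
- the description of cough change as natural history;
- the later-visit accuracy of reflex cough sensitivity as a marker of swallowing dysfunction (Hypothesis 4), if management alters PAS but not cough sensitivity.

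If start dates and reasons are not collected prospectively, no later analysis can reliably separate these effects.

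**Working it through.** **1. Timeline against data collection.**

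| Step | What the plan provides |
|---|---|
| Visit 1 fluoroscopy (or the Protocol 1 examination) | Possible referral (Section 8) |
| 10 to 18 months | Management could start; no planned record of it |
| Visit 2 fluoroscopy | Outcome measured; possible further referral |
| 10 to 18 months | As above |
| Visit 3 fluoroscopy | Outcome measured |

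Baseline PAS is in the model and partly predicts who is referred after visit 1. It does not show who was treated, when, or with what effect, and it cannot reflect a referral prompted by visit 2.

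**2. The plan's own sample size.** The Protocol 2 power analysis gives PAS changes from baseline for "the first two 10 to 14 months period are 2.08 (1.97) and 2.82 (2.33), respectively", and, "to reach a 0.85 power by controlling the type I error rate to 0.05 for detecting this effect size with two-sided test", concludes that "we would need 155 PD patients".

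- Contrast: 2.82 − 2.08 = 0.74.
- SD of the paired difference with within-patient correlation 0: √(1.97² + 2.33²) = √9.31 = 3.05.
- Normal approximation: ((1.960 + 1.036) × 3.05 / 0.74)² = 152.6, so 153.
- Paired t-test (noncentral t): 155, with power 0.851.

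The stated 155 is reproduced, so there is no arithmetic error here. The point concerns data collection and what the estimate means.

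**3. When unrecorded management would move the contrast.** Let s2 and s3 be the average shifts in PAS change from baseline, at visits 2 and 3, due to management. The contrast becomes 0.74 + (s3 − s2).

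- If s2 = s3, the contrast and its power do not change, although both mean changes are shifted.
- If s3 is more negative than s2, for instance because more people are under management by visit 3, the contrast shrinks.
- If s2 is more negative, it grows.

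**4. Illustration only.** The documents give no uptake or effect. Assume that 10 to 30% are managed, that their PAS is 0.5 to 1.0 point lower, and that this affects the later change only. Reduction = proportion × effect. Power is for the two-sided paired t-test at n = 155. With correlation 0.5, the SD is √(9.31 − 2 × 0.5 × 1.97 × 2.33) = 2.17.

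| Assumed managed × effect | Contrast | Power, correlation 0 | Power, correlation 0.5 |
|---|---|---|---|
| none | 0.74 | 0.85 | 0.99 |
| 10% × 0.5 | 0.69 | 0.80 | 0.98 |
| 20% × 0.5 | 0.64 | 0.74 | 0.95 |
| 20% × 1.0 | 0.54 | 0.59 | 0.87 |
| 30% × 1.0 | 0.44 | 0.43 | 0.71 |

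The table shows how sensitive the contrast would be in an unfavourable case. It does not estimate what will happen.

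**The case against.** **Referral is conditional.** Section 8 expects no direct benefit for most participants, says only that the examination may find something, and limits this to people without a prior clinical study. Clinical and research fluoroscopy can also stand in for each other, so some referrals would have occurred in usual care anyway. This stands: the documents support saying that changes may be affected by treatment, not that they are.

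**Natural history is claimed for cough only.** A reader might infer that PAS change is also presented that way. It is not; the term is used once, for cough function.

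**Hypothesis 4 does not predict faster decline at 10 or more years.** A reader might infer that treating late-stage patients would mask such a decline. The hypothesis predicts differences over three time points and, at 10 or more years, that reflex cough sensitivity is an accurate marker of swallowing dysfunction.

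**The effect on power is not established.** It is tempting to divide an assumed shift in mean PAS by 0.74 and call the result a loss of effect. That sets a shift in level against a contrast between two changes. Any power loss needs an unequal effect on those changes, and it is smaller with positive within-patient correlation. The pilot patients may also have received swallowing care, in which case its effect is already in 2.08 and 2.82.

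**Other sources exist.** The team reviews medical records, and the health history questionnaire might ask about therapy (its appendix is not in the text available). But the questionnaire is described as an eligibility tool, and the listed record items do not include therapy. Neither is a planned between-visit record.

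The boluses are fixed, so a changed home diet does not alter what is tested. That narrows the routes by which management could act but does not remove them.

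**Conclusion.** The gap is real and follows from the text alone: possible referral after a study examination, 10 to 18 months before the next outcome, and no exclusion, per-visit record or analysis strategy for swallowing or cough management. As written, the plan cannot separate disease course from selectively given treatment in Aim 4, and the unqualified natural-history wording for cough is not supported.

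The size and direction of any bias in the contrast are unknown. The stated sample size is reproduced and is not called into question by this point. The power figures above rest on assumed uptake, assumed benefit, an effect on the later change only, and an assumed correlation. The documents do not support saying that Aim 4 is underpowered for this reason or that participants' outcomes have been altered. This is a cheap improvement worth making before follow-up data are collected, because the information is hard to recover afterwards.

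**What to change.** Leave referral as it is.

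1. Add to the Protocol 2 per-visit list any swallowing or cough therapy or other dysphagia management, with type, start date and whether a study finding prompted it. Collect this at all three visits, including therapy already under way at visit 1. Where the Protocol 1 examination serves as visit 1, collect it there.
2. Keep the mixed model on all data as the main analysis. Describe its estimate as change under care that includes study-triggered referral, and replace the unqualified natural-history wording in the expected-outcomes text accordingly.
3. Add a supportive mixed model restricted to observations before such management began. Report both estimates with confidence intervals. Do not rely on a simple therapy covariate: therapy follows from earlier PAS, so its coefficient would be confounded by indication.

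The cost is a few questions per visit and one extra model. That model has fewer observations and assumes that the start of management is explained by observed data, so it supports the main analysis and does not replace it.
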